#### 8.3.1 Protocol Defined Adverse Events of Special interest

The following adverse events are defined as of special interest.

- a sudden and clinically important increase in oxygen requirements
- a rapid decline in clinical status leading to intubation and mechanical ventilation
- clinically important increases in inflammatory markers

• Neuropsychiatric AEs

Adverse events of interest will be summarized using counts and percentages and a Listing will be provided.

### 8.4 Clinical Laboratory Tests

Laboratory assessments, providing indication of safety, include serum chemistry (Glucose, Blood Urea Nitrogen, Sodium, Chloride, Creatinine, Potassium, Calcium, Uric Acid, Total Protein, Albumin, Total Bilirubin, Alkaline Phosphatase, Aspartate Aminotransferase, Alanine Aminotransferase, Bicarbonate) and hematology (Red blood cell count, Hemoglobin, Hematocrit, Platelets, White blood cell count, Neutrophils, Lymphocytes, Monocytes, Eosinophils, Basophils), and will be collected during Screening visit and then once weekly at Day 7 and Day 14 visits. Urinalysis is scheduled to be collected only in Screening visit.

Laboratory results will be assessed versus normal ranges (provided locally for each site) and abnormal results will be further classified as clinically significant (Yes/No). In addition, results will be graded using the NCI CTCAE v5.0 criteria.

Chemistry and Hematology laboratory tests will be presented at baseline, Day 7 and Day 14 visits. Laboratory tests results and changes from baseline to each visit will be summarized using descriptive statistics for continuous variables.

The incidence of abnormal results and of clinically significant abnormal results will be summarized for laboratory data using frequencies and percentages, per analyte and timepoint, including 'any time post-baseline' time point.

Shifts (below, within, and above the normal range) from baseline to each visit and 'any time post-baseline' will be summarized using patient counts. Similarly, shifts in interpreted result (normal, abnormal high clinically significant result, and abnormal low clinically significant) will be provided. In shift analysis to any time during study, the worst outcome in both directions (Low, High) will be considered (A subject may be counted both as a shift to High and as a shift to Low, if experienced both events during the study).

In addition, laboratory tests will be summarized by maximal toxicity grade.

Denominators for percentages will equal the number of subjects in the safety population providing data for specific time point.

Listings for clinically significant abnormal laboratory data will be presented.

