#### 9.2 Exclusion Criteria

- 1) Any co-morbidity that may add risk to the treatment in the judgement of the investigator.
- 2) Requiring intubation and mechanical ventilation
- 3) Patient having a do not intubate or do not resuscitate order
- 4) Oxygen saturation >95% on room air

- 5) Any preexisting respiratory condition that requires intermittent or continuous ambulatory oxygen prior to hospitalization
- 6) Patient is, in the investigator's clinical judgement, unlikely to survive >72 hours
- 7) Pregnant (positive serum test within 3 days prior to randomization) or nursing women
- 8) Unwillingness or inability to comply with procedures required in this protocol.
- 9) Corrected QT (QTc) interval on electrocardiogram (ECG) >470 ms for females or >450 ms for males, calculated using Friedericia's formula (QTcF)
- 10) AST (SGOT) or ALT (SGPT) > 5 x upper limit of normal (ULN)
- 11) Bilirubin >2x ULN (except where bilirubin increase is due to Gilbert's Syndrome)
- 12) Serum creatinine >2.0 X ULN
- 13) Absolute neutrophil count <1000 cells/mm^3
- 14) Platelet count <75,000/mm^3
- 15) Hemoglobin < 8.0 g/dL
- 16) Currently taking medications that are sensitive CYP3A4, CYP1A2, CYP2C9, CYP2C19 or CYP2D6 substrates and have a narrow therapeutic index. These should be decided in discussion with the Medical Monitor on a case-by-case basis.
- 17) Currently taking medications that are strong inducers or inhibitors of CYP2D6 and CYP3A4. These should be decided in discussion with the Medical Monitor on a case-by-case basis.
- 18) Currently taking warfarin, apixaban, argatroban or rivaroxaban
- 19) Current drug or alcohol abuse
- 20) Currently participating in a clinical study assessing pharmacological treatments, including antiviral studies

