# 15.4 Laboratory Abnormalities

All new abnormal laboratory findings and those abnormal at baseline which change significantly (i.e., by at least one toxicity grade as defined in the National Cancer Institute Common Terminology Criteria for Adverse Events [NCI CTCAE] v5.0) are considered AEs. Laboratory AEs for which there is no clinical intervention will be recorded only on the laboratory data pages of the eCRF. Laboratory AEs not listed in the NCI CTCAE v5.0 will be considered as grade 1 (mild) if there is no clinical effect or intervention. Laboratory values outside the normal range for certain parameters will not be considered AEs if they are generally not considered as indicating an abnormality; this includes such parameters as liver enzymes which are below the normal range. If there is a clinical sequela or intervention, the laboratory abnormality is to be graded according to the criteria used for clinical AEs, described above.

The NCI CTCAE v5.0 can be downloaded in pdf format at:

 $https://ctep.cancer.gov/protocolDevelopment/electronic\_applications/docs/CTCAE\_v5\_Quick\_Reference\_8.5x11.pdf$ 

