14.3.3.1.2	Chemistry Normal/Abnormal and Clinically Interpretations Results by Visit and at 'Any Post Baseline Time by Treatment Group	Safety
14.3.3.1.3	Shift from baseline to each Visit and 'any time post baseline' for Chemistry Abnormal Values by Treatment Group and Overall	Safety
14.3.3.1.4	Shift From Baseline to each Visit and 'any time post baseline' for Chemistry Clinically Interpreted Test Results, by Treatment Group	Safety
14.3.3.2.1	Hematology Results and Change from Baseline by Visit and by Treatment Group	Safety
14.3.3.2.2	Hematology Normal/Abnormal and Clinically Interpretations Results by Visit and at 'Any Post Baseline Time Point' and by Treatment Group	Safety
14.3.3.2.3	Shift from baseline to each Visit and 'any time post baseline' for Hematology Abnormal Values by Treatment Group and Overall	Safety
14.3.3.2.4	Shift From Baseline to each Visit and 'any time post baseline' for Hematology Clinically Interpreted Test Results, by Treatment Group	Safety
14.3.3.3	Incidence of laboratory toxicity by maximal toxicity grade during study by Treatment Group	Safety
14.3.4.1	Vital signs Results and Change from Baseline by Visit and Treatment Group	Safety
14.3.4.2	Vital Signs Clinically Interpretations Results at any time during study by Treatment Group	Safety
14.3.5.1	ECG Normal/ ABNORMAL and Clinically Interpretations Results by visit and time point by Treatment Group	Safety
14.3.5.2	ECG Normal/ ABNORMAL and Clinically Interpretations Results by visit and time point by Treatment Group for Subjects on concomitant Hydroxychloroquine	Safety: subjects on concomitant Hydroxychloroq uine
14.3.6	Concomitant medications by WHO Dictionary ATC Level 4 and PT by Treatment Group	Safety
14.3.7	Hospitalization by Treatment Group	Safety

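### The laboratory toxicity table uses the maximal grade without the baseline grade, so abnormalities already present at entry can be counted as toxicity

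*SAP*

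**What the plan says.** SAP section 8.4 first sets the scale: "In addition, results will be graded using the NCI CTCAE v5.0 criteria". It then says "In addition, laboratory tests will be summarized by maximal toxicity grade". The matching output in SAP section 12, Table 14.3.3.3, is titled "Incidence of laboratory toxicity by maximal toxicity grade during study by Treatment Group". Neither place mentions the baseline grade, worsening or treatment emergence.

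Section 8.4 also plans laboratory outputs that do refer to baseline: continuous changes from baseline at Day 7 and Day 14; "Shifts (below, within, and above the normal range) from baseline to each visit" and to any time after baseline; and shifts in the investigator's clinical-significance reading.

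Protocol section 15.4 defines which laboratory findings are adverse events: "All new abnormal laboratory findings and those abnormal at baseline which change significantly (i.e., by at least one toxicity grade" under CTCAE v5.0. It adds: "Laboratory AEs for which there is no clinical intervention will be recorded only on the laboratory data pages of the eCRF".

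Protocol section 9.2 sets the entry limits. The liver-enzyme exclusion, for instance, is "AST (SGOT) or ALT (SGPT) > 5 x upper limit of normal (ULN", so values between 1 and 5 times ULN may enter.

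**The concern.** A table whose title speaks of the incidence of laboratory toxicity will be read as showing what happened on treatment. Hospitalised COVID-19 patients may arrive with abnormal chemistry or haematology, and the entry limits allow it. If the table takes the highest grade regardless of the starting grade, a stable entry abnormality and a new one can fall in the same cell. Two errors are then possible. A chance imbalance at entry can look like a drug effect, or a real difference can be diluted by carried-in grades.

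Two parameters deserve a clean table. Protocol section 6.4.1.1 names creatinine and lymphocytes as the exceptions to the absence of consistent laboratory trends in the solid-tumour study. Creatinine up to 2 x ULN may enter, and section 9.2 sets no lymphocyte limit.

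The recording rule in Protocol section 15.4 adds weight. Laboratory adverse events without intervention stay on the laboratory pages, and the SAP has no step that applies the one-grade rule to them. Table 14.3.3.3 is the only summary by grade that the SAP clearly plans from those pages.

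**Working it through.** The documents state no figure on this point, so there is nothing to reproduce. The check is mainly textual; the arithmetic is an illustration.

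**Does any text tie the maximal grade to baseline?**
- SAP 8.4 and the title of Table 14.3.3.3: no.
- SAP 5.1: its post-baseline convention covers clinically significant abnormal values and does not mention grades.
- Neighbouring titles in SAP section 12 (14.3.3.1.2 to 14.3.3.1.4 and 14.3.3.2.2 to 14.3.3.2.4) specify post-baseline values or a shift from baseline. The title of 14.3.3.3 does neither.
- Even if *during study* in that title means after the first dose, an entry abnormality that persists to Day 7 or Day 14 is still counted.

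**Do the other outputs separate carried-in from worsened grades?**
- Range shifts have three levels, so a rise from 2 x to 8 x ULN is high at both ends.
- Clinical-significance shifts rest on the investigator's call, not on grade.
- Means of change in about 20 patients per arm can hide a few who worsen.

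Each output helps in part. None sets baseline grade against worst grade.

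**Illustration.** From the documents: n = 20 per arm (SAP 3.3). Assumed: a proportion p of patients enter with a graded abnormality in one analyte; it persists; the table is read as any grade, yes or no. The minimisation factors (SAP 3.4) are age, HbA1c and oxygen requirement, so entry status for other analytes is left to chance.

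*Expected count per arm*, with a true worsening rate q = 10% (assumed):
- Maximal-grade count = 20 x [p + (1 - p) x q]
- Count under the one-grade rule = 20 x q = 2.0

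*Chance imbalance*: P(|X - Y| >= 4), with X and Y independent Binomial(20, p), computed exactly.

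*Dilution* of a true 10% versus 40% contrast: (1 - p) x 30 points.

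| p (assumed) | Maximal-grade count | One-grade rule | Excess | P(difference >= 4 of 20) | 30-point contrast appears as |
|---|---|---|---|---|---|
| 10% | 20 x 0.19 = 3.8 | 2.0 | 1.8 | 0.063 | 27 points |
| 30% | 20 x 0.37 = 7.4 | 2.0 | 5.4 | 0.226 | 21 points |
| 50% | 20 x 0.55 = 11.0 | 2.0 | 9.0 | 0.268 | 15 points |

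**The case against.** The best case for the plan has five parts.

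1. *A reader might infer that the table breaches Protocol 15.4.* It does not. That section says when a laboratory finding is an adverse event; it does not prescribe laboratory tables, and Protocol 17.4 leaves the detail of the safety analyses to the SAP. What remains is a mismatch: the protocol describes worsening in grades, and no planned summary shows it that way.

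2. *A reader might infer that baseline grades will be ignored.* The SAP is silent rather than explicit. In its shift paragraph, *any time during study* refers to the post-baseline analysis, and SAP section 12 says the final output list is kept in study files. So entry abnormalities can be counted as toxicity; the text does not establish that they will be. This objection stands as a limit on wording.

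3. *A reader might want a worked ALT case*, in which a patient entering at 4 x ULN and improving to 3.5 x ULN is tabulated like one rising from normal. That depends on CTCAE thresholds, and on whether they refer to baseline. The documents do not reproduce them, so the example cannot be relied on. Nor do the entry limits show how many patients start with a graded value; they show only what is permitted.

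4. *A reader might infer that laboratory events without intervention never reach the TEAE tables.* Protocol 15.4 fixes where they are recorded. SAP 8.3 does not expressly limit its summaries to AE-page entries. The supportable statement is that the SAP gives no derivation for them.

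5. The table is by grade, so a rise from grade 1 to grade 3 appears under grade 3. The any-grade calculation above therefore overstates the blurring for patients who change category. This stands too.

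Full chemistry and haematology listings are also planned, so a careful reader could reconstruct individual cases.

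**Conclusion.** The point holds as a gap in safety reporting. The plan sets no baseline condition for the maximal-grade summary, plans no shift by CTCAE grade, and admits abnormal values at entry. Followed literally, it can report persisting entry abnormalities as laboratory toxicity, and it leaves the protocol's one-grade rule without any step in the analysis.

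The size cannot be fixed from the documents. The imbalance probabilities of about 6%, 23% and 27% have correct arithmetic, but they rest on assumed entry prevalence, on persistence and on an any-grade reading. They show the direction and possible scale, not a property of this trial.

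The consequence is minor. The study is descriptive, SAP 5.3 rules out inferential use of p-values, and no efficacy result, criterion for stopping study drug or DSMB trigger uses this table.

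**What to change.** In SAP section 8.4 and Table 14.3.3.3:

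- State that the maximal grade is taken over post-baseline values only, with baseline as defined in SAP 5.2.
- Present the table per analyte, and per direction where both high and low values are graded, as baseline grade by worst post-baseline grade.
- Add a count of patients whose worst post-baseline grade is new or at least one grade above baseline.
- State how laboratory adverse events recorded only on the laboratory pages are derived, and whether they enter the TEAE tables.
- Keep the plain maximal-grade count as a supplementary table or listing.

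The cost is SAP wording and some table programming; the values are collected and the grading is already planned. The headline counts will be lower than in the plain table, so a footnote should give the counting rule.

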# 8.5 Vital Signs

Vital signs (temperature, blood pressure, pulse rate, respiratory rate and oxygen saturation by pulse oximeter) will be collected during screening visit, at Day 1, and daily whilst the subject is hospitalized, at End of treatment visit and at Safety follow-up visit.

Summary statistics for vital signs values and changes from baseline will be presented at baseline (Day 1), and at each scheduled visits (Day 2-13, end of treatment, safety follow up). The incidence of clinically significant abnormal values will be summarized for selected vital signs using descriptive statistics.

A listing for clinically significant abnormal vital signs will be presented.

### 8.6 Supplemental oxygen requirement

Supplemental oxygen requirement outcome is the target of the primary efficacy endpoint (refer to section 3.2.1. Listings of all supplemental oxygen requirement evaluation will also be provided. Figures will be provided as possible.

## 8.7 Electrocardiography

12-lead electrocardiogram will be performed for all subjects during screening visit and at Day 14 visit. For patients on concomitant hydroxychloroquine, the 12-lead ECG will be repeated after 3 hours ( $\pm 30$ mins) of initial dose, on Day 2 and Day 4.

Incidence of abnormal result and of abnormal clinically significant results will be summarized using appropriate descriptive statistics. Summaries may be provided separately for the subjects on concomitant hydroxychloroquine.

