## **6.4.1 Completed Studies**

#### 6.4.1.1 Phase 1b Study in patients with advanced solid tumors (Study No. ABC-101)

Twenty-two patients were enrolled, of whom 21 were treated with doses from 250 mg QD through 750 mg BID. All 21 patients were evaluable for pharmacokinetics, pharmacodynamics and safety. Sixteen were evaluable for efficacy per RECIST 1.1 criteria. Patients received treatment continuously in 28

day cycles and treatment was given while fasting. Mean age of patients entered was 58 years. Seventy one percent were male, 67% white. All patients had received prior chemotherapy and approximately half had prior surgery and/or radiotherapy. Patients had a variety of concomitant medical conditions and were receiving a variety of medications in addition to their antitumor therapy.

The administered oral dose of 500 mg Q12 hours was the maximum tolerated dose. There were no deaths reported during the administration of opaganib. There were no discontinuations due to adverse events (AEs), in 250 mg QD and 250 mg bid cohorts. Common adverse events were nausea (12 patients, 57%), fatigue (12 patients, 57%), vomiting (8 patients, 38%) and neuropsychiatric effects (14 patients, 67%) including anxiety, insomnia, agitation and dysarthria. Of these, only fatigue appeared to be dose-related. Nausea and vomiting were common but not dose-limiting and rarely required discontinuation of treatment. Neuropsychiatric effects were seen at all dose levels, though were more common and bothersome at the highest dose level, 750 mg Q12 hours, considered an intolerable dose.

There were no consistent trends toward increases or grade shifts in liver function tests, hematologic parameters, or other biochemical parameters except for creatinine and lymphocytes. No patient developed clinically significant ECG abnormalities on study. There were no treatment group differences noted for the changes from baseline of QTcF. For more detailed data refer to Investigator Brochure.

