# 12.1.4 The following will be monitored less frequently as part of standard of care and wherever possible

- For patients on concomitant hydroxychloroquine, a 12-lead electrocardiogram (if allowed by hospital treatment guidelines under COVID-19) approximately 3 hours after the first study drug administration on Day 1, anytime on Days 2 and 4, and again at end-of-treatment (either Day 14, 28 or at premature study drug discontinuation). If patients are on monitors (including telemetry or Holter monitors), investigators are encouraged to collect QT interval data
- Nasopharyngeal or oropharyngeal viral swab for SARS-CoV-2 PCR test every 1-3 days
- Serum chemistry once weekly
- Serum CRP, D-Dimer, LDH, ferritin, cardiac troponin once weekly
- CBC with differential once weekly
- Chest X-ray as per physician decision

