### 6.7 Electrocardiography

Electrocardiogram findings (normal, abnormal, and missing) at baseline will be summarized using appropriate descriptive statistics, and will be presented for the Safety population.

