# **Individual Patient Data Listings**

Listing Number	Title	Population
16.2.1.1	Patients Disposition	All Screened Patients

Listing Number	Title	Population
16.2.1.2	Patients Not Eligible for the Study	All Screened Patients
16.2.1.3	Patient Disposition with reasons for early termination of treatment and early termination of study	ITT
16.2.2	Demographic and Baseline Characteristics	ІТТ
16.2.3	Covid-19 Disease History	ITT
16.2.4	Medical History	ITT
16.2.5	Prior Medication	ITT
16.2.6	ECG	Safety
16.2.7	Abnormal Physical Examinations	Safety
16.2.8	Protocol Violations	All Screened Patients
16.2.9	Supplemental oxygen requirement and AUC	mITT
16.2.10	Viral swab for SARS-CoV-2 PCR test	mITT
16.2.11.1	Systemic markers of inflammation results	mITT
16.2.11.2	Abnormal systemic markers of inflammation	mITT
16.2.12	Secondary End Points by Subject Derivations	mITT
16.2.13.1	Study Drug Exposure	Safety
16.2.13.2	Study Drug Compliance	Safety
16.2.14.1	All Adverse Events	Safety
16.2.14.2	Adverse Events Resulted in Death	Safety
16.2.14.3	Serious Adverse Events	Safety
16.2.14.4	Adverse Events Leading to Treatment Withdrawal	Safety
16.2.14.5	Special Interest Adverse Events	Safety
16.2.15.1	Chemistry Results	Safety
16.2.15.2	Abnormal Clinically Significant Chemistry Results	Safety
16.2.15.3	Hematology Results	Safety
16.2.15.4	Abnormal Clinically Significant Hematology Results	Safety
16.2.16.1	Vital Signs Results	Safety
16.2.16.2	Clinically Significant Vital Signs	Safety
16.2.17.1	ECG Results	Safety
16.2.17.2	Abnormal ECG Results	Safety
16.2.18	Abnormal Physical Examination	Safety
16.2.19	Abnormal X-Ray Results	Safety

Listing Number	Title	Population
16.2.20	Concomitant medications	Safety
16.2.21	Hospitalization	Safety

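### The SAP plans no summary of QTcF values, changes or outliers, so a small or moderate QT shift that does not turn an ECG reading abnormal could go unseen

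*SAP*

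**What the plan says.** **Planned ECG summaries.** All are categorical.

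- SAP 6.7, baseline: "Electrocardiogram findings (normal, abnormal, and missing) at baseline will be summarized using appropriate descriptive statistics".
- SAP 8.7, after baseline: "Incidence of abnormal result and of abnormal clinically significant results will be summarized using appropriate descriptive statistics".
- SAP 12, Table 14.3.5.1: "ECG Normal/ ABNORMAL and Clinically Interpretations Results by visit and time point by Treatment Group". Table 14.3.5.2 repeats this for patients on hydroxychloroquine.
- SAP 12 also plans ECG listings (16.2.6, 16.2.17.1 and 16.2.17.2) but does not specify their contents.

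**Where the protocol uses QT.**

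- Protocol 9.2 excludes patients with a QTc "interval on electrocardiogram (ECG) >470 ms for females or >450 ms for males", by the Fridericia correction.
- Protocol 12.1.4, in the bullet on ECGs for hydroxychloroquine patients, says that where patients are on monitors "investigators are encouraged to collect QT interval data".
- Protocol 6.4.1.1, on the sponsor's solid-tumour study: "There were no treatment group differences noted for the changes from baseline of QTcF".

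**ECG as an endpoint.** Protocol 13.4 and SAP 3.2.4 list ECG among the safety endpoints without naming a parameter. Protocol 17.4 leaves the detail of the safety analyses to the SAP.

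**Timing.** Under SAP 8.7 all patients have an ECG at screening and Day 14. Those on hydroxychloroquine have further ECGs about 3 hours after the first dose and on Days 2 and 4.

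**The concern.** The plan obtains a numeric QTcF for every patient in order to decide eligibility, and then has no numeric use for it. An abnormal/normal count pools QT with every other ECG finding, and SAP 8.7 gives no rule for what counts as abnormal. The same SAP treats comparable safety data differently: laboratory tests (8.4) and vital signs (8.5) are both summarized as values and as changes from baseline.

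At stake is how the ECG safety endpoint will be read. A table with few abnormal ECGs in either arm could be taken as evidence of no QT effect, alone or with hydroxychloroquine, when it was not built to show a shift in the interval. QT is the only ECG parameter named in the hydroxychloroquine bullet, yet any QT data collected there have no planned summary.

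**Working it through.** The documents give no ECG sample size, power or event count, so there is no stated figure to reproduce. The check has three parts.

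**1. Headroom below the protocol's own limits** (450 ms men, 470 ms women; Protocol 9.2)

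- Baseline 400 ms: a man can rise 450 − 400 = 50 ms and a woman 470 − 400 = 70 ms without exceeding the limit.
- Baseline 420 ms: 30 ms and 50 ms.

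A yes/no reading at limits of this kind can hide a sizeable within-patient rise.

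**2. What a mean-change summary would show**

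Input from the documents: 20 per arm (SAP 3.3). Assumption: SD of QTcF change 12 to 25 ms. All 40 patients are taken to contribute, which is optimistic.

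- SE = SD × √(2/20). For SD 20, SE = 6.32 ms.
- 95% CI half-width = t(0.975, 38 df) × SE = 2.024 × 6.32 = 12.8 ms.
- Approximate power at two-sided 0.05 = Φ(shift/SE − 1.96). For a 20 ms shift with SD 20: Φ(3.16 − 1.96) = 0.885.

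| Assumed SD (ms) | CI half-width (ms) | Power, 10 ms | Power, 20 ms | Power, 30 ms |
|---|---|---|---|---|
| 12 | 7.7 | 75% | >99% | >99% |
| 15 | 9.6 | 56% | 99% | >99% |
| 20 | 12.8 | 35% | 88% | >99% |
| 25 | 16.0 | 24% | 72% | 97% |

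**3. What a count above a limit would show**

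Assumptions: mean QTcF without a drug effect 410 or 420 ms; on-treatment SD 18 or 25 ms; normal distribution; one cut at 450 ms for everyone. P(above 450) = 1 − Φ((450 − mean − shift)/SD). Power is exact for Fisher's test with 20 per arm.

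| Mean, SD (ms) | P, no shift | P, 20 ms shift | Power, 10 ms | Power, 20 ms | Power, 30 ms |
|---|---|---|---|---|---|
| 410, 18 | 0.013 | 0.133 | 0.2% | 9% | 63% |
| 410, 25 | 0.055 | 0.212 | 2.5% | 18% | 55% |
| 420, 18 | 0.048 | 0.289 | 5% | 43% | 90% |
| 420, 25 | 0.115 | 0.345 | 7% | 30% | 69% |

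Fisher's test is conservative at these counts. The normal approximation gives 30% to 53% for a 20 ms shift, still below the 72% or more from means.

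A clean table also says little: with 0 of 20 abnormal, the two-sided 95% upper limit is 1 − 0.025^(1/20) = 16.8%.

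The trial plans no formal tests, so these powers only measure how readily each summary would show a shift.

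**The case against.** **Other routes exist, and this stands.** A reader might infer that any QT effect would be missed. The documents do not support that. Protocol 15.5 requires clinically significant ECG changes to be recorded as adverse events. SAP 8.3 grades these by CTCAE and tabulates them by preferred term, so a reported QT event would have its own line. ECG listings are planned. Even the crude count above 450 ms has 55% to 90% power at a 30 ms shift. However, adverse-event recording applies its own judgement of clinical significance, and the listings give no comparison between arms. Small and moderate shifts therefore remain exposed.

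**QT collection is not a requirement.** A reader might infer that sites must supply QT data. The protocol only encourages it, for monitored patients, within the hydroxychloroquine bullet and under a heading qualified by feasibility. Nor does SAP 8.7 say who classifies the ECG, so reliance on the investigator's reading is an inference.

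**The 450 ms cut is not in the SAP.** This stands. The SAP leaves abnormal undefined, and the protocol's limit for women is 470 ms. No single fraction of lost information can be claimed.

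**A Day 14 mean could mislead too.** This stands. Patients not on hydroxychloroquine have one scheduled post-baseline ECG. Those discharged off oxygen take study drug only to Day 10, so their Day 14 ECG is off drug. This is a reason to split the summary.

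**Prior data and unseen documents.** The solid-tumour study found no QTcF group differences and no clinically significant ECG abnormalities, in 21 treated patients at up to 750 mg twice daily. That lowers the urgency but does not exclude an effect. The case report forms are not available here, and SAP 12 says the final table list is kept in study files, so a QTcF table may exist there. The SAP as written does not call for one.

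**Conclusion.** The concern holds in a limited form. The SAP plans no summary of QTcF values, change from baseline or outlier categories, although QTcF decides eligibility. A small or moderate shift that does not turn a reading abnormal could go unseen; marked prolongation would still have several ways to surface.

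The size is illustrative only. For a 20 ms shift, mean change gives about 88% power at SD 20 ms (72% to over 99% across SD 25 to 12 ms), against about 9% to 43% for counts above 450 ms. For a 10 ms shift, mean change at SD 20 ms gives about 35% and the counts at most 7%, so the proposed summary would often be inconclusive there too. These figures rest on assumed means, SDs and cut-off, and on all 20 patients per arm having a usable ECG.

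The absence of formal hypotheses (SAP 5.3) does not answer the point, because what is missing is a description. It is a cheap, worthwhile improvement and does not affect the efficacy conclusions.

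**What to change.** In SAP 8.7, with a matching table in SAP 12, add:

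- QTcF value and change from baseline by arm and time point, with a 95% CI for the difference between arms, using the QTcF obtained for eligibility as baseline.
- Counts of QTcF outliers, by value and by increase from baseline, at limits fixed before unblinding. The protocol's sex-specific eligibility limits can serve as one set.
- The same summaries for patients on hydroxychloroquine.
- Day 14 results shown separately for patients still on study drug and those already off it.
- A separate listing of monitor-derived QT, not pooled with 12-lead values.
- A statement of whether the eCRF holds the interval, and the number of patients contributing at each time point.

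Use only ECGs already done, where the interval is recorded or retrievable. If the blind has already been broken, report the summary as an addition in the study report, as SAP 1 and 3.5.2 provide.

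Separately, the end-of-treatment ECG days for hydroxychloroquine patients must be reconciled. The protocol synopsis gives Day 10, Day 14 or premature discontinuation; Protocol 12.1.4 gives Day 14, Day 28 or premature discontinuation. The Schedule of Assessments marks Day 14 and has no ECG under early termination.

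Cost: one extra table, and transcription from source where only the reading was entered. With about 15 sites and the SAP finalized just before unblinding, that retrieval is the larger part of the work.
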